## **Introduction**

In the United States, approximately 1.1 million persons are living with HIV. Despite novel pharmacological breakthroughs, comprehensive models of health care, and targeted HIV testing initiatives, over 160,000 persons are still unaware of their HIV serostatus. Emerging adult, sexual minority, men of color are disproportionately affected. Premised on the National AIDS Strategy's focus on identifying new HIV infections through increased HIV testing, the purpose of this formative pilot study is to develop and test an integrated HIV self-testing strategy that utilizes a simplicity-model approach to HIV self-testing in emerging adult sexual minority men of color.

The overall study will focus on: (a) understanding facilitators and barriers to HIV self-testing among emerging adult MSM, (b) designing a HIV self-testing infographic that utilizes a simplicity model, (c) finalizing the HIV self-testing infographic with input from a leadership group of HIV community members, (d) conducting a pilot clinical trial with 300 emerging adult (ages 18-34), sexual minority, men of color to test if a collaboratively-designed HIV self-testing infographic can facilitate accurate and effective understanding of how to self-test for HIV when compared to paper-based, HIV self-testing information.

By conducting this study, we will gain beneficial insights necessary for presenting HIV self-testing instructions in a meaningful, relevant, and comprehensible way. The results of this pilot study have the potential to inform strategies regarding how self-testing instructions can be worded or visually presented in order to break both literacy and language barriers that affect testing utilization and results accuracy.

## **Methods**

The HOTIE intervention was a sequential, mixed methods pilot randomized controlled trial. Mixed methods were an appropriate study design as we sought to describe the context for needing to develop an HIV self-testing infographic and the process of steps that lead to testing

of the infographic. The study methods are consistent with the approaches for conducting mixed methods research by Curry and Nunez-Smith.

Participants were recruited online from a HIPAA-compliant data management national survey panel recruitment company. Participants were screened for eligibility online. Once considered eligible, they were informed about the purpose, risks and benefits of the study and then completed an online consent to participate or decline to participate. Those who consented to participate were then randomly assigned, using automated random selection to either the intervention group (HIV self-testing infographic) or to the control group (HIV self-testing text-based instructions). The primary outcome was comprehension of the HIV Self-testing Infographic and Usefulness, Ease of Use, Ease of Learning and Satisfaction of the HIV Self-testing Infographic. Health literacy was a secondary outcome. More detailed information on the development and design of the infographic can be found elsewhere.

## **Measures**

Sociodemographic data collected will include age (in years), gender, sexual attraction, race-ethnicity, educational attainment, employment status, annual income, and other information to characterize the sample. Outcomes of interest include health literacy, oral HIV self-testing knowledge, HIV knowledge, oral HIV self-testing infographic usability as well as PrEP use, familiarity, and attitudes. The following instruments will be administered.

***Oral HIV self-testing knowledge.*** Oral HIV self-testing knowledge will be assessed using an Oral HIV self-testing questionnaire. The Oral HIV self-testing questionnaire will assess accuracy in using oral HIV self-testing kits. Correct responses will be coded as “1” and incorrect responses “0”. Responses to the five-items will be summed to yield a total Oral HIV self-testing knowledge score ranging from 0 to 5.

**Oral HIV self-testing infographic usability questionnaire.** The Oral HIV self-testing infographic usability questionnaire is a 14-item measure designed to assess usefulness and usability of the HIV oral self-testing infographic. The Oral HIV self-testing infographic usability questionnaire was derived from the Usefulness, Satisfaction, and Ease Questionnaire[1]. Responses will be recorded using a 7-point Likert scale ranging from *strongly disagree* (1) to *strongly agree* (7). This measure assessed four domains that included usefulness of the HIV oral self-testing infographic (M = 5.47, SD = 1.40; Cronbach's  $\alpha$  = .92), ease of use of the HIV oral self-testing infographic (M = 5.51, SD = 1.23; Cronbach's  $\alpha$  = .85), ease of learning using the HIV oral self-testing infographic (M = 5.41, SD = 1.37; Cronbach's  $\alpha$  = .86), and satisfaction with the HIV oral self-testing infographic (M = 5.34, SD = 1.33; Cronbach's  $\alpha$  = .79). Responses to the 14-item measure will be summed to yield a mean score on usability among experimental group participants only ranging from 15 to 98.

**Health literacy.** The Short Assessment of Health Literacy-English, or SAHL-E is an 18-item measure designed to assess an English-speaker's ability to read and understand common medical terms [2]. The test contains a printed common medical term, a key word (the correct response), and a distractor word. Responses will be recorded dichotomously with either *false* (0) or *true* (1). Prior studies have demonstrated good internal consistency ranging from .80 to .89 [2]. Responses to 18-items will be summed to yield a total score on Health literacy ranging from 0 to 18. Higher scores indicate greater health literacy.

**HIV knowledge.** The Brief HIV Knowledge Questionnaire (HIV-KQ18)[3] is an 18-item true or false response measure that distinguishes understanding about HIV transmission, prevention, and consequences. Correct responses will be coded as "1" with incorrect responses coded as "0". Prior studies have demonstrated good internal consistency ranging from 0.75 - 0.89 [3]. The measure has been identified as suitable for those with low health literacy [3]. Responses to the 18-items will be summed to yield a total score on HIV knowledge ranging from 0 to 18.

**PrEP Use, Familiarity, and Attitudes.** PrEP Use, Familiarity, and Attitudes will be assessed using three separate multiple-choice questions. PrEP use will be assessed using the question: “PrEP is the use of a medication taken before having sex as protection against HIV infection. Are you currently taking PrEP?” and measured dichotomously (0 = No, 1 = Yes). PrEP familiarity will be assessed using the question: “Truvada is a pill that HIV negative people can take to prevent HIV. This is called PrEP or Pre-Exposure Prophylaxis. How familiar are you with Truvada also called PrEP?” Responses will be collected using a three-item Likert scale from 1 (not familiar or I do not know about PrEP) to 3 (Familiar or I know about PrEP). PrEP attitudes will be measured using the question “How do you feel about HIV-negative people taking Truvada as PrEP to prevent transmission of HIV?” Responses will be collected using a four-point Likert scale from 1 (extremely negative) to 4 (extremely positive).

**Statistical Analysis Plan.** Post-hoc power analysis estimates will be performed using G\*Power [4]. Analyses indicated that based on a type I error rate set at .05 and conservative effect size of .4 [5], and sample of 322 participants randomly assigned to experimental and control groups in this RCT study, we will have .95 power to reject the null hypothesis with our oral HIV self-testing knowledge questionnaire [5]. Analyses will be conducted in STATA. Between-group differences will be examined using chi-square and independent samples t-tests to determine significant sociodemographic differences. Between-group differences using independent samples t-tests will also be examined on outcomes including oral HIV self-testing knowledge, HIV knowledge, and health literacy. Cases with missing data will be excluded from the analyses.

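### Does the wrong range (15 to 98) and the summed "will be summed to yield a mean score on usability among experimental group participants only ranging from 15 to 98" wording leave the usability outcome without a usable score?

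*Combined protocol and SAP*

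**What the plan says.** In the Combined protocol and SAP, the usability paragraph of Measures gives the make-up of the scale: "The Oral HIV self-testing infographic usability questionnaire is a 14-item measure", and "Responses will be recorded using a 7-point Likert scale ranging from" 1 (strong disagreement) to 7 (strong agreement).

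It then lists four domains, each with a mean and SD:

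- "usefulness of the HIV oral self-testing infographic (M = 5.47, SD = 1.40"
- "ease of use of the HIV oral self-testing infographic (M = 5.51, SD = 1.23"
- "ease of learning using the HIV oral self-testing infographic (M = 5.41, SD = 1.37"
- "satisfaction with the HIV oral self-testing infographic (M = 5.34, SD = 1.33"

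The scoring rule closes the paragraph: responses "will be summed to yield a mean score on usability among experimental group participants only ranging from 15 to 98".

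Methods names, as part of the primary outcome, "Usefulness, Ease of Use, Ease of Learning and Satisfaction of the HIV Self-testing Infographic", alongside comprehension. The Statistical Analysis Plan section names oral self-testing knowledge, HIV knowledge and health literacy for the between-group t-tests. It ties the power statement to the knowledge questionnaire and drops cases with missing data. It does not mention usability.

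**The concern.** Three things in one short paragraph do not fit together. The stated minimum cannot be the minimum of 14 items scored from 1. The rule uses both sum and mean for one score. The domain statistics sit on a scale on which 15 to 98 has no meaning.

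Methods lists four constructs, while the only scoring rule pools all 14 items. The documents do not give the number of items per domain, the domain scoring rule, or which score is primary.

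If these points mattered, a primary outcome could be reported as one total or as four domain scores, on either scale, with the choice made after seeing the data. Two practical harms also suggest themselves: a valid score of 14 might be rejected as out of range, and a raw sum would fall when a respondent skips an item.

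**Working it through.** **Inputs.** 14 items, scored 1 to 7, stated range 15 to 98, and domain means 5.47, 5.51, 5.41 and 5.34 (all from Measures). The complete-case rule, 322 participants, effect size 0.4 and power 0.95 come from the Statistical Analysis Plan section.

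**1. The stated range.** The range of a sum is k × 1 to k × 7.

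- k = 14: 14 to 98, width 84.
- k = 15: 15 to 105.
- 14 items scored 0 to 6: 0 to 84.

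None of these gives 15 to 98. The upper bound is right and the lower bound is one point too high, which is 1/84 = 1.2% of the range.

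**2. The scale of the domain means.** If they were domain sums, the 14-item total would be 5.47 + 5.51 + 5.41 + 5.34 = 21.73, or 21.73/14 = 1.55 per item. That is close to strong disagreement throughout and is implausible. They are almost certainly item means on 1 to 7, although the text does not say so.

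**3. Sum against item mean.** With all 14 items answered, sum = 14 × item mean, and the SD scales by the same factor. The equal-weight average of the domain means is 21.73/4 = 5.43, which is 14 × 5.4325 = 76.1 as a sum. Any standardised quantity is identical on the two scales.

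**4. Total against domains.** The 14-item mean is an average of the domain means weighted by items per domain. The weights are not given, so take every split with at least 2 items per domain.

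- Lowest: 8 × 5.34 + 2 × (5.47 + 5.51 + 5.41) = 75.50, or 5.39 per item.
- Highest: 8 × 5.51 + 2 × (5.47 + 5.41 + 5.34) = 76.52, or 5.47 per item.

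The four domain means themselves span only 5.51 − 5.34 = 0.17.

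**5. Skipped items.** Summing over the answered items only would lose about 5.43 points per skipped item, 5.43/84 = 6.5% of the range. The complete-case rule removes such a respondent from the analysis, so no deflated sum is analysed.

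**6. Out-of-range rejection.** The documents describe no range check or validation rule that would reject a score of 14.

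**7. What depends on the score.** The scoring rule restricts usability to the infographic arm, so no between-group comparison of it is possible. The power figure comes from other inputs: with 161 per arm (equal allocation assumed), effect size 0.4 and two-sided 0.05, power is 0.948 (normal approximation) or 0.947 (t-test), which agrees with the stated 0.95. No usability number enters it.

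**The case for a change.** The best case for a change rests on how the endpoint is defined. Methods names four domains in the primary outcome, Measures defines one pooled score, and the Statistical Analysis Plan section leaves usability out. An analyst could report either and claim to have followed the plan, and one added sentence would close the gap at almost no cost. Nor is 15 likely to be an observed minimum: the other summed scales give possible ranges (0 to 5 for five items, 0 to 18 for 18 items, twice), and those are all correct.

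Much of this stands. The bound is wrong, the sum/mean wording is loose, and the documents do not say how domain scores are formed or which score leads. What does not follow is a consequence. A questionnaire can yield four domain scores and a total without contradiction. The analysts have already formed and summarised all four domains, so the missing rule has been filled in the obvious way. Freedom to choose after the data are seen matters when the choice can turn a result; here there is no comparison, no significance test and no success threshold, and the candidate summaries nearly coincide.

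A reader could also take the mean score as the group mean of summed scores. That would ease the sum/mean point but not the range error.

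**Conclusion.** The text contains a clerical slip (14, not 15), a loose word, and an omission about domain scoring. None of them calls for a change to the plan. There are two scales, not three, and in complete cases they differ by a factor of 14. The choice between total and domains is worth at most 0.17 of a point on a 1 to 7 scale. No test, power figure or conclusion depends on the bound or the scale, because usability is a descriptive outcome in one arm.

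This rests on four assumptions: the complete-case rule is applied to usability as to the other outcomes; the printed domain means are item averages, which their size strongly supports; those means resemble the ones the trial will report, since their source is not stated; and each domain has at least 2 items, which affects only the 75.50 to 76.52 interval. If usability were later compared between arms or held to a cut-off, the primary score and its scale would need to be fixed in advance; nothing in the current plan does either.

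### The oral HIV self-testing knowledge score is compared only by an unadjusted t-test although age and education are collected: a cheap, modest gain in precision is left unused (minor)

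*Combined protocol and SAP*

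**What the plan says.** The Statistical Analysis Plan paragraph (at the end of Measures) gives the whole outcome analysis in one sentence: "Between-group differences using independent samples t-tests will also be examined on outcomes including oral HIV self-testing knowledge, HIV knowledge, and health literacy". No section names a covariate, an adjusted model or a stratification factor. Of the outcomes, only knowledge has a power claim: "we will have .95 power to reject the null hypothesis with our oral HIV self-testing knowledge questionnaire", at a type I error of .05, an effect size of .4 and 322 participants.

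For baseline data the same paragraph says: "Between-group differences will be examined using chi-square and independent samples t-tests to determine significant sociodemographic differences". It does not say what follows from a significant or a non-significant result. Measures gives the purpose of these data, which include age, as "educational attainment, employment status, annual income, and other information to characterize the sample". Methods says that the arms are formed by random assignment.

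The missing-data rule is one line: "Cases with missing data will be excluded from the analyses".

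**The concern.** Age and educational attainment may predict how many of five questions about using a self-test kit a person answers correctly. If they do, a comparison that ignores them has a wider confidence interval than the data allow. The values are collected anyway, so the precision would come without new data. It can be claimed for the main analysis only if the model is fixed in advance.

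The baseline tests raise a smaller, separate matter of reporting. Among all randomised participants any difference between arms is due to chance. Among analysed participants it need not be, because cases with missing data are dropped. The plan does not say which set is tested, and a p-value does not separate the two causes. With no rule attached, a significant result might also prompt an adjustment that was never planned.

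**Working it through.** **Inputs.** From the Statistical Analysis Plan: alpha .05, effect size .4 (read as a standardised difference), N = 322. Assumed: two-sided test and 1:1 allocation, 161 per arm. The documents state neither.

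**1. Reproduce the planned power.** The noncentrality is .4 × √(161/2) = 3.589 on 320 degrees of freedom. Two-sided power from the noncentral t is .947, which agrees with the stated .95. A one-sided test would give .974, which does not. The unadjusted 95% CI half-width is 1.967 × √(2/161) = .219 SD.

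**2. Add covariates.** If they explain a share R² of the outcome variance, the residual variance is multiplied by (1 − R²). Estimating k covariate terms costs a factor (N − 3)/(N − k − 3). With k = 5 (for example age, three contrasts for four education levels, and one missing category; the number of levels is not in the documents) this is 319/314 = 1.0159. The variance factor is V = (1 − R²) × 1.0159, the effective effect size is .4/√V, and the half-width is .219 × √V.

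| Assumed R² | V | .4/√V | Power | Half-width (SD) |
|---|---|---|---|---|
| unadjusted | 1 | .400 | .947 | .219 |
| .02 | .996 | .401 | .948 | .219 |
| .05 | .965 | .407 | .954 | .215 |
| .10 | .914 | .418 | .963 | .210 |
| .20 | .813 | .444 | .978 | .198 |

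**3. Break-even.** V = 1 when R² = k/(N − 3): 2/319 = .006 for two terms and 5/319 = .016 for five. If R² were zero, five terms would widen the half-width to .219 × √1.0159 = .221 SD.

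**4. The smaller sample size.** The Introduction gives 300 participants. Unadjusted power is then .932. With the cost factor 297/292 = 1.0171 it is .933/.940/.950/.969 at the same four R² values.

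**5. Missing education.** Suppose 5% or 10% of cases lack education (assumed; the documents give no rate), leaving about 306 or 290, and take R² = .05.
- Regression dropping those cases: half-width .221 or .227 SD.
- t-test also dropping them: 1.968 × √(2/153) = .225, or 1.968 × √(2/145) = .231 SD.
- t-test keeping everyone: .219 SD.
- Regression with a missing category, keeping everyone: about .215 SD at either rate.

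The regression figures come from a simulation with 2,000 runs per setting, age uniform on 18-34, four education levels and education missing at random. In it the missing-category model had type I error .043 to .059, against .044 to .062 for the t-test.

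**6. Baseline tests.** Measures names seven sociodemographic variables. If all seven are tested at .05 and the tests are independent, the chance of at least one false difference is 1 − .95⁷ = .30; for five tests it is 1 − .95⁵ = .23. Education, employment and income are plausibly correlated, so these figures are only indicative.

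**The case against.** **The t-test is a legitimate choice.** This stands. Randomisation makes it valid, and leaving out covariates does not bias the comparison. A reader might infer that the planned comparison is confounded or has the wrong error rate; nothing in the documents supports that.

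**The gain is small and may not exist.** This largely stands. At R² of .02 the net gain in power is about .001 (.947 to .948). The documents give no R², and the 18-34 age range may limit what age explains. The study is also a pilot, although one with a .95 power claim on this outcome.

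**The exclusion rule could cancel the gain.** A reader might infer that adjustment would widen the interval, because .221 or .227 SD exceeds .219. That holds only if cases lacking education leave the regression but stay in the t-test. The rule can equally mean that they leave every analysis, and then the t-test is the wider of the two (.225 or .231 SD). The text does not settle which is meant. A missing category avoids the issue.

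**It may be too late.** Methods is in the past tense ("The HOTIE intervention was a sequential, mixed methods pilot randomized controlled trial"), the power paragraph opens "Post-hoc power analysis estimates will be performed using", and Measures prints a usability result: "usefulness of the HIV oral self-testing infographic (M = 5.47, SD = 1.40". A reader might conclude that outcome data have been seen. The documents do not establish this, since most of Measures and the analysis paragraph is in the future tense. The fix must therefore cover both cases.

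**Baseline p-values do no harm.** They change no planned estimate, because no decision depends on them. This stands, and it is why they are only a reporting point.

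**Conclusion.** The point holds as a minor, inexpensive improvement. With R² between .05 and .20, pre-specified adjustment would raise power from .947 to between .954 and .978 and narrow the half-width from .219 SD to between .215 and .198 SD. At R² of .02 it would change almost nothing, and below about .006 to .016 it would lose slightly.

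This rests on a two-sided test, equal arms, a standardised effect of .4, five covariate terms and an R² that the documents do not give. It also requires that recorded age and education, including whether education is missing, are not affected by arm; the documents do not say when these data are collected. The sociodemographic tests are a secondary matter of reporting. They answer no stated question, but they do not damage the outcome comparison.

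**What to change.** **If outcome data have not been seen:** pre-specify a linear regression of the knowledge score on arm, age and educational attainment, with a missing category for education so that no case is dropped for a covariate. Report the arm difference with its 95% CI and keep the unadjusted t-test as a supporting analysis. State when age and education are collected and confirm that this cannot depend on arm. Do not add health literacy as a covariate without clarification: Methods lists it as a secondary outcome, and its timing is not given.

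**If outcome data have been seen:** keep the t-test as the planned analysis and label the adjusted estimate as not prespecified.

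**In either case:** replace the sociodemographic significance tests with a descriptive table by arm (means and SDs, percentages) for all randomised participants with data, and the same table for those analysed. Together these show differential exclusion directly.

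**Cost:** a few lines of plan text, one extra model and one extra table, with a small loss of precision if R² is near zero. No new survey item is needed, although participants who leave early may lack some sociodemographic values.
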